### 5.8 TREATMENT COMPLIANCE

Each subject or parent/caregiver will record the dose, dosing frequency and IMP consumption in the subject's diary. Subjects will bring their used, partially used, and unused IMP to every study visit. Treatment compliance will be monitored by measuring the volume of IMP in these bottles and comparing to the dispensation log and diary records.

### 6. VISIT SCHEDULE

Study procedures will be conducted according to the Schedule of Assessments in Table 1. Time windows for all assessments are detailed in Table 6.

Confidential Page 50 of 175

**Table 6:** Time Windows for Assessments

Visit / Procedure	Time window (relative to scheduled visit / procedure)
Visit 1 (Clinic; Study Day -43 to -42 or -42 to -41):	Not applicable
Visit 2 (Phone; Study Day -21)	± 3 days
Visit 3 (Clinic; Study Day -1; Randomization)	+ 4 days ^a
Visits 4, 5 (Phone: Study Days 4, 8)	± 3 days
Visit 6 (Clinic; Study Day 15)	± 4 days
Visit 7 (Phone: Study Day 29)	± 4 days
Visit 8 (Clinic; Study Day 43)	± 4 days
Visit 9 (Phone: Study Day 57)	± 4 days
Visit 10 (Clinic; Study Day 71)	± 4 days
Visit 11 (Phone: Study Day 85)	± 4 days
Visit 12 (Clinic: Study Day 99)	± 4 days
Visit 13 (Clinic; Study Day 113; post dosing)	± 4 days
Visit 14 (ECHO clinic; 3-6 months after last dose)	+ 30 days
Blood collection for ZX008 PK	± 15 minutes
Blood collection for AED concentration	Prior to morning dose of AED medication

AED=antiepileptic drug (s); ECHO=echocardiogram; PK = pharmacokinetics

# 6.1 BASELINE PERIOD (STUDY DAY 42 TO STUDY DAY -1)

The Baseline Period of the study encompasses the screening activities that will occur on Study Day -42 as well as the observation period where subjects will be assessed for baseline seizure activity based on recordings of daily seizure activity entered into a diary.

### 6.1.1 Screening, Clinic Visit 1 (Study Day -42)

Screening is the predetermined series of procedures with which each investigator selects an appropriate and representative sample of subjects for enrollment into the study. Select screening data will be documented in the IVR/IWR and eCRF.

Written informed parental or guardian consent and assent of minors (if the subject is capable of providing assent) must be obtained before a subject can start any of the screening procedures. The procedure(s) for obtaining written informed consent and assent of minor (if the subject is capable of providing assent) are described in Section 11.2.

The Screening visit will occur on Study Day -42; however, the procedures may be split over 2 consecutive days (e.g., Study Day -43 and Study Day -42 or Study Day -42 and Study Day -41). Splitting the visit procedures across 2 nonsequential days requires the approval of the medical monitor. The following procedures will be performed for all subjects before the start of seizure activity observation:

- Obtain written informed consent for the study
- Obtain written informed consent from parent/caregiver to collect PedsQL Family Impact, HADS, and EQ-5D-5L ratings of parent/caregiver symptoms and quality of life

Confidential Page 51 of 175

In cases where the screening period is extended beyond 42 days, the immediate 42 days before the Randomization visit will be used to calculate the baseline seizure frequency

- Review inclusion and exclusion criteria
- Record demographic information
- Record medical, neurological, and epilepsy history
- Record current epilepsy status (number/type/duration seizures per month)
- Collect past 6 months (or available duration) of parent/caregiver seizure diary data if available (screen shots of cell phones are acceptable, as are photocopies of paper diaries or print outs) and place in source file
- Record prior medications
- Complete physical examination, including height, weight, and calculation of BMI
- Complete neurological examination
- 12-lead electrocardiogram
- Doppler ECHO (this may be obtained any time between Study Day -42 and Study Day -21)
- Vital signs
- Urine pregnancy test for females of child-bearing potential
- Laboratory evaluation (serum chemistry, hematology, urinalysis, etc)
- Urine THC panel
- Whole blood CBD
- Obtain blood sample for epilepsy genotype panel
- C-SSRS Children's Baseline/Screening Assessment (Appendix 2)
- Instruct parent/caregiver on use of diary
- Dispense diary (after above procedures have been concluded)
- Record AEs
- Record AESIs

Only eligible subjects as specified by the inclusion and exclusion criteria with an independently confirmed diagnosis of DS by the Epilepsy Study Consortium will be enrolled into the study.

After enrollment into the study, each subject will be issued a "Subject Card" containing information about the subject's participation in the study. The subject or parent/caregiver will be advised to retain this card on his person for the entire duration of the study so that the investigator or the sponsor can be contacted in case of emergency.

In certain circumstances the sponsor may allow subjects who did not meet all inclusion/exclusion criteria at the time of the Screening Visit to have the screening period extended, or to be re-screened for eligibility. In all cases the investigator should consult with the Medical Monitor. Decisions whether to permit rescreening resides solely with the sponsor.

The decision whether to permit extended screening or rescreening can be influenced by many factors individual to that subject case. Some general principles apply:

1. If baseline seizure screening is extended or the subject is discontinued and then rescreened, the screening period for establishing the baseline seizure frequency will be the immediate 6 weeks

Confidential Page 52 of 175

before the randomization visit.

- 2. Subjects who are found to be on a prohibited medication at the screening visit may be weaned off of that medication provided:
  - a. Decisions to withdraw a disallowed concomitant medication must be made with the agreement of the prescribing physician
  - b. If the medication has antiepileptic properties, a wash out of at least 5 half-lives must be completed before collection of baseline seizure data.
  - c. If a decision has been made to wean off of a medication without antiepileptic properties and the wash-out period (at least 5 half-lives) is expected to be shorter than 5 weeks, then the subject may remain in screening and chart seizures using the seizure diary.

# 6.1.2 Phone Visit 2 (Study Day -21)

Site personnel will contact the subject via telephone on Study Day -21 and record the following:

- AEs
- AESI

In addition, site personnel with review the diary entries with the parent/caregiver.

# 6.1.3 Clinic Visit 3 (Study Day -1): Randomization

This period is intended to ensure that subjects meet the study entry criteria and confirm they have experienced ≥6 convulsive seizures during the 6-week Baseline Period, with at least 2 seizures in each 3-week half of the Baseline Period. Subjects must have at least 42 days of prospective diary data at Visit 3. Subjects will report to the clinic in the morning on Study Day -1 to allow for plasma sample collection for AED pharmacokinetic evaluation prior to the morning dose of these medications. Subjects should not take their morning dose(s) of AED medication prior to reporting to the clinic.

The following procedures will be performed on Study Day -1:

- Review inclusion and exclusion criteria
- Review current seizure activity (number/type/duration) from diary since previous visit and calculate the number of convulsive seizures during the first 3 weeks, the second 3 weeks, and over the full 6-weeks of the observation period.
- Record prior medications since previous visit
- Complete physical examination, including height and weight, and calculation of BMI
- Abbreviated neurological examination
- Vital signs
- 12-lead ECG
- Urine pregnancy test for females of child-bearing potential

Confidential Page 53 of 175

- Laboratory evaluation (serum chemistry, and hematology, and urinalysis)
- aixeling authori Collect plasma sample for AED pharmacokinetic evaluation prior to the morning dose of study medication(s)
- Urine THC panel
- Whole blood CBD
- Tanner Staging for subjects >7 years of age (Appendix 5)
- Collect and review diary with parent/caregiver
- Dispense diary
- C-SSRS Children's Since Last Visit Assessment (Appendix 2)
- BRIEF (Appendix 3)
- QOLCE (Appendix 4)
- PedsQL (Appendix 6)
- PedsQL Family Impact module (Appendix 6)
- Parent/Caregiver QoL using the EQ-5D-5L scale (Appendix 7
- Affective symptoms of parent/caregiver using the HADS scale (Appendix 8)
- Record AEs
- Record AESI
- When eligibility for the Titration Period is confirmed, randomize (blinded) subject to treatment assignment (ZX008 0.2 mg/kg/day, ZX008 0.8 mg/kg/day, or placebo)
- Dispense study medication (If administration of the first dose of study medication occurs in the clinic, the next dose should be at least 8 hours later or the following morning. The dose on the following morning will count as Study Day 1.)

#### 6.2 TITRATION AND MAINTENANCE PERIODS

#### 6.2.1 **Titration Period Study Day 1**

Subjects will take their first dose of study medication on the morning of Study Day 1. Study Day 1 is considered the first day of dosing, even for those subjects that received an in-clinic dose on Study Day -1.

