### Titration + Maintenance (T+M) Period

The T+M period combines the Titration and Maintenance periods, beginning on Study Day 1 and extending through Study Day 99. The T+M period is considered the treatment period.

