# 10.5.2 Safety Analyses

Summaries of safety data will be presented by treatment – ZX008 0.8 mg/kg/day, ZX008 0.2 mg/kg/day or placebo – separately for the Titration, Maintenance and T+M periods. The number and percentage of subjects in each treatment group with AEs will be displayed by body system and preferred term using the Medical Dictionary for Regulatory Activities (MedDRA). Summaries of AEs by severity and relationship to study drug will also be presented. A separate summary will be provided for all serious AEs (SAEs). Selected summaries will be repeated broken out by age group, ie, for ages <6 years and ≥6 years.

Hematology and chemistry laboratory results will be summarized using shift tables that tabulate the

Confidential Page 85 of 175

proportion of subjects who have lab results that change from baseline. Shift tables will be presented for each time point where lab results are collected. Mean change from baseline will also be calculated for continuous hematology and chemistry results at all time points available.

Laboratory tests, vital signs, physical examinations, neurological examinations, ECG, Doppler echocardiogram, C-SSRS, Tanner Staging results, etc, will be summarized appropriately, by treatment. All safety summaries will be based on the SAF Population.

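### A permitted in-clinic first dose on Day -1 comes before every named safety summary period, so adverse events between that dose and Day 1 are recorded but belong to no period (minor)

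*Protocol*

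**What the plan says.** - **Protocol 6.1.3 (Visit 3, Day -1).** After randomization, study medication is dispensed, with a note for subjects who receive their initial dose at the visit: "the next dose should be at least 8 hours later or the following morning". A second dose on Day -1 is therefore possible. The section adds: "The dose on the following morning will count as Study Day 1".
- **Protocol 6.2.1.** "Subjects will take their first dose of study medication on the morning of Study Day 1". The next sentence reads: "Study Day 1 is considered the first day of dosing, even for those subjects that received an in-clinic dose on Study Day -1".
- **Protocol 10.4.** The Titration Period begins on Day 1, described there as the first day of treatment. T+M, which the section calls the treatment period, is defined as "beginning on Study Day 1 and extending through Study Day 99". Baseline is the span of about 42 days before randomization and the start of treatment.
- **Protocol 6.1, heading.** "BASELINE PERIOD (STUDY DAY 42 TO STUDY DAY -1" (the minus sign before 42 is missing here but present in the table of contents). On this wording the Baseline Period includes Day -1.
- **Protocol 10.5.2.** Safety summaries are presented by treatment, "separately for the Titration, Maintenance and T+M periods".

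**The concern.** The start of exposure and the start of the analysis periods can differ. A subject dosed in clinic on Day -1 is exposed before the Titration, Maintenance and T+M periods begin. Events in the first hours after a supervised first dose are among those a safety reviewer most wants to see against treatment. Hypersensitivity reactions, which Section 8.8 singles out for reporting within 72 hours, are an example. If the period definitions are applied literally, such an event is not tabulated in any named period, and in a listing ordered by study day it looks like a pre-treatment event.

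There is a smaller consistency problem for efficacy. The protocol does not settle whether seizures after a Day -1 dose are baseline seizures or belong to no period. Subjects dosed in clinic and subjects first dosed at home would then have slightly different period boundaries.

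**Working it through.** **Step 1. Place an event in the periods.** Take an adverse event that begins on Day -1, some hours after an in-clinic dose.

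- Titration starts on Day 1 (10.4): the event is outside.
- Maintenance starts on Day 16 (10.4): outside.
- T+M starts on Day 1 (10.4): outside.
- AE collection starts at informed consent (8.4): the event is recorded.
- The Safety Population needs one dose, with no condition on the day (10.2.1): the subject is included.

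So the event is captured and the subject counted, but none of the periods named in 10.5.2 contains the event. Visit 3 is a morning visit and the next dose may follow after 8 hours, so the gap can hold up to two doses. About 24 hours is an upper bound, since dosing comes after the visit procedures.

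**Step 2. Compare with the anchor used elsewhere.** Section 8.6 separates early serious events by first exposure to study drug. Section 8.1.1 distinguishes events before administration from those after it. Section 5.7 classes medication as concomitant once the first administration has taken place, but as prior therapy if taken during the baseline assessment. If Baseline includes Day -1, rescue medication given after a Day -1 dose meets both descriptions. These sections work from actual exposure; 6.2.1 and 10.4 work from the day number.

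**Step 3. Place a seizure in the periods.** Under the 6.1 heading, a seizure after dosing on Day -1 is a baseline seizure. Under 10.4 it is in neither Baseline nor T+M. The rule for extended or repeated screening in 6.1.1 uses the 6 weeks before the randomization visit, which agrees with 10.4.

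**Step 4. Size the efficacy effect on the less favourable reading (Day -1 counted as baseline).** First, the plan's own figure. With a difference of 40 points, SD 50, two-sided alpha 0.05 and 90% power (10.1):

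n per arm = 2 × (1.960 + 1.282)² × (50/40)² = 32.8, so 33 (about 34 with the t distribution). At the planned 35 per arm, power is 0.917 (0.910 with the t distribution). The stated 35 and 90% reproduce.

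Now assume that h hours on drug are counted in a 42-day baseline, and that a 40% reduction (e = 0.4) acts from the first dose.

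- On-drug share of baseline: f = h / (24 × 42)
- Observed baseline relative to true: b = 1 − f × e
- Measured reduction: 1 − (1 − e) / b

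| h | f | b | measured reduction |
|---|---|---|---|
| 8 | 0.79% | 0.9968 | 39.8% |
| 24 | 2.38% (1/42) | 0.9905 | 39.4% |

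The largest shift is 40 − 39.4 = 0.6 points. Using 39.4 as the between-arm difference at 35 per arm gives power 0.910 against 0.917. This treats every active subject as dosed in clinic, with an immediate full effect and no shift on placebo, so it is a worst case.

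**The case against.** The strongest reply is that nothing is lost. Adverse events are collected from consent, the Safety Population counts any dose, Section 10.5 says that all safety data will be summarized, and 10.5.2 adds a separate summary of serious events. A treatment-emergent definition is normally written in the SAP, which is not shown and could start at the actual first dose. The sentence in 6.2.1 is also deliberate: Amendment 2 added it, and it keeps the titration steps and visit days aligned for all subjects. In-clinic dosing is conditional; the default is a first dose on the morning of Day 1.

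Most of this stands, and it limits the point. A reader might infer that first-dose events disappear from the safety record. They do not: they are recorded, and 10.5.2 does not say that its three periods are the only presentation. A reader might also infer that baseline seizure frequency contains on-drug time. Only the 6.1 heading supports that; the statistical definition in 10.4 and the screening rule in 6.1.1 do not. Nor does the 6.2.1 sentence have to go, because it works as a numbering rule.

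The reply does not remove the point. The protocol is not silent and waiting for an SAP. It fixes the first day of dosing, the period starts and the safety summary periods, and together these leave the gap. An SAP that follows them inherits it; one that anchors on actual first dose departs from the period start the protocol sets.

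**Conclusion.** The point holds as a minor inconsistency in period definitions, mainly affecting how early safety events are attributed. For each subject dosed in clinic on Day -1, adverse events from that dose to the start of Day 1 are recorded but fall in none of the named safety summary periods. The protocol does not say how often sites dose in clinic, so the number affected could be anywhere from 0 to all 105.

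The baseline question is one of consistency only. Even if the post-dose hours count as baseline, they are at most 2.4% of baseline time and move an assumed 40% reduction by about 0.6 points. That figure rests on a full day on drug and an immediate effect. The primary comparison is not threatened. The conclusion rests on the protocol text alone; an SAP that anchors safety on actual first exposure would close the gap in practice, though the protocol wording would still need to agree with it.

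**What to change.** - In 6.2.1, keep Day 1 as the numbering convention for the titration and visit calendar, and say that this is its purpose.
- In 6.2.1, 10.4 and 10.5.2, state that for analysis the safety treatment period starts at the date and time of the actual first dose, including an in-clinic dose on Day -1.
- In 10.4, state that baseline seizure data end before the first dose, and bring the 6.1 heading into line.
- Reconcile the two adjacent sentences of 6.2.1 with 6.1.3, since the first places the initial dose on Day 1 without exception.

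The cost is a few sentences of wording and a recorded time for the first dose. No visit or subject is added, and when dosing is allowed does not change.

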#### 6.2.2 Phone Visits 4 and 5 (Titration Period Study Days 4 and 8)

Site personnel will contact the subject via telephone on Titration Period Study Days 4 and 8 and record the following:

- AESI
- Concomitant medications

In addition, site personnel will review study medication dosing procedure and the diary entries with the parent/caregiver.

#### 6.2.3 **Clinic Visit 6 (Titration Period Study Day 15)**

Confidential Page 54 of 175 Subjects will report to the clinic in the morning on Titration Period Study Day 15. Subjects should not take their morning dose(s) of AED medication prior to reporting to the clinic. The following procedures will be performed:

- Review current seizure activity (number/type/duration) from diary since previous visit
- Record concomitant medications
- Abbreviated physical examination, including height and weight, and calculation of BMI
- Abbreviated neurological examination
- Obtain vital signs
- Urine pregnancy test for females of child-bearing potential
- Laboratory evaluation (serum chemistry and hematology, and urinalysis)
- Urine THC panel
- Whole blood CBD
- Collect plasma sample for AED pharmacokinetic evaluation prior to the morning dose of study medication(s)
- Collect and review diary with parent/caregiver
- Dispense diary
- C-SSRS Children's Since Last Visit Assessment (Appendix 2)
- Clinical Global Impression Improvement (assessed by parent/caregiver)
- Clinical Global Impression Improvement (assessed by investigator)
- Record AEs
- Record AESI
- Collect used, partially used and unused study medication; perform drug accountability and review with parent/caregiver
- Dispense study medication

### 6.2.4 Phone Visit 7 (Maintenance Period Study Day 29)

Site personnel will contact the subject via telephone on Maintenance Period Study Day 29 and record the following:

- AEs
- AES
- Concomitant medications

In addition, site personnel with review the diary entries with the parent/caregiver.

### 6.2.5 Clinic Visit 8 (Maintenance Period Study Day 43)

Subjects will report to the clinic in the morning on Maintenance Period Study Day 43. Subjects should not take their morning dose(s) of study medication and AED medication prior to reporting to the clinic. The following procedures will be performed:

- Review current seizure activity (number/type/duration) from diary since previous visit
- Record concomitant medications

Confidential Page 55 of 175

- Abbreviated physical examination, including height and weight, and calculation of BMI (Note: if the subject's weight is ±25% of the weight at Study Day-1, the IMP dose will be recalculated)
- Obtain vital signs
- 12-lead electrocardiogram
- Doppler ECHO (this must be obtained any time between Study Day 40 and Study Day 54)
- Urine pregnancy test for females of child-bearing potential
- Laboratory evaluation (serum chemistry and hematology, and urinalysis)
- Urine THC panel
- Whole blood CBD
- Collect plasma sample for ZX008 pharmacokinetic evaluation at the following timepoints: within 1 hour prior to the morning dose of study medication, and 1, 2 and 4-6 hours after the morning dose of study medication
- Collect plasma sample for AED pharmacokinetic evaluation prior to the morning dose of study medication(s)
- Collect and review diary with parent/caregiver
- Dispense diary
- C-SSRS Children's Since Last Visit Assessment (Appendix 2)
- BRIEF (Appendix 3)
- QOLCE (Appendix 4)
- PedsQL (Appendix 6)
- Affective symptoms of parent/caregiver using the HADS scale (Appendix 8)
- Clinical Global Impression Improvement (assessed by parent/caregiver)
- Clinical Global Impression Improvement (assessed by investigator)
- Record AEs
- Record AESI
- Collect used, partially used and unused study medication; perform drug accountability and review with parent/caregiver
- Dispense study medication

### 6.2.6 Phone Visit 9 (Maintenance Period Study Day 57)

Site personnel will contact the subject via telephone on Maintenance Period Study Day 57 and record the following:

- AEs
- AESI
- Concomitant medications

In addition, site personnel with review the diary entries with the parent/caregiver.

### 6.2.7 Clinic Visit 10 (Maintenance Period Study Day 71)

Confidential Page 56 of 175

Subjects will report to the clinic on Maintenance Period Study Day 71. The following procedures will be performed:

- Review current seizure activity (number/type/duration) from diary since previous visit
- Record concomitant medications
- Abbreviated physical examination, including height and weight, and calculation of BMI
- Obtain vital signs
- Urine pregnancy test for females of child-bearing potential
- Laboratory evaluation (serum chemistry and hematology, and urinalysis)
- Urine THC panel
- Whole blood CBD
- Collect and review diary with parent/caregiver
- Dispense diary
- C-SSRS Children's Since Last Visit Assessment (Appendix 2)
- Clinical Global Impression Improvement (assessed by parent/caregiver)
- Clinical Global Impression Improvement (assessed by investigator)
- Record AEs
- Record AESI
- Collect used, partially used and unused study medication; perform drug accountability and review with parent/caregiver
- Dispense study medication

At Clinic Visit 10, compliant subjects who have tolerated IMP should be presented with the ICF for the open-label extension study. Informed consent for the open-label extension study must be signed at Visit 12 or earlier in order to enter the open-label extension study.

